5.6 Data Analysis

- Provide sample size determination and analysis (include anticipated rate of screen failures, study discontinuations, lost to follow-up etc.).
- Describe how, where and by whom the data will be analyzed.

Sample size calculations:

The sample sizes shown in each arm and sub-arm in Figure 3, above, were determined by the proportions of patients in participating clinics with the conditions or behaviors of interest. Table 3, below, provides that information, starting with the sizes of the clinic populations, drawn from the CDW. Note that for blood pressure and Hgb A1c we include the baseline rates of patients who meet BOTH the criteria of a specific threshold of poor control AND repeat measurement within a 6-month window, since six months is the window we plan to use for follow up assessment of the efficacy of the intervention compared with control.

Table 3: Clinical characteristics of participating clinical sites in 2018

	Chicago	Cleveland
Primary care clinic population (2 visits in past 2 years)	32,791	11,796
Diabetes clinic population	1,245	1073
Total	34,036	12,833
Primary care + Diabetes		
Most Recent SBP>140 or DBP>90* with repeat in < 6 Mo	10,959 (32%)	1513 (12%)
Proportion of Days Covered*	88%	84%
Return Visit Adherence**	93%	94%
Diabetes Clinic only		
Hgb A1c>8 with repeat in< 6Mo	821 (66%)	751 (70%)

*A measure of medication adherence from the CDW: proportion of days patients had pills to cover medication needs based on refill rate over a 120 day interval.

**A measure of appointment adherence from CDW: The percentage of all visits scheduled to any clinics by patients seen in these clinics in 2018.

Determining the specific sample sizes shown in the flow diagram from the data in table 3 required determining the power needed to test each hypothesis with at least 80% power to detect the expected effect.

We describe next the planned analysis for testing each hypothesis to achieve each aim:

Aims 1 and 2:

As summarized in Table 4, we will apply several measures to assess the effectiveness of the intervention, testing hypotheses to achieve Aims 1 and 2. For each hypothesis, comparisons between arms will be made using mixed-effect linear or logistic regression as appropriate for the outcome, with a fixed effect of study arm, VA site, and primary vs. secondary care setting, and a random effect of provider to accommodate clustering of visits within providers. Of primary interest is the direction, magnitude, and significance of the regression coefficient associated with study arm. Primary analysis will compare arms on an intention-to-treat basis, without regard to whether audio made available in Arm 1 is actually accessed by anyone; secondary analyses will include covariates representing whether, how often, and by whom (patient or provider) audio is actually accessed in Arm 1 to assess the impact of audio use (vs. availability). As patients will be randomized to arms, we do not expect demographic or other patient differences among arms, but will conduct tests for differences, and if any variables differ significantly among arms, we will include them as covariates in the regression models.

Table 4. Hypotheses and evaluation strategy for effectiveness of intervention (Aims 1 and 2)

Hypothesis	Evaluation Strategy
1A: OAA increases patient activation.	Administer PAM (Appendix A-1) 1-2 weeks post visit via phone call and compare scores in Arm 1 vs. Arm 2
1B: OAA increases care plan adherence, including fewer no-shows and more on-time refills.	Utilizing the data warehouse measure Return Visit Adherence (RVA) and refill rates (PDC) ^{24,32,33} in Arms 1 vs. 2.
1C: OAA reduces Hgb A1c and BP	Same as above: Utilizing data warehouse measure A1c and BP.
2A: Providers obtain higher scores on measures of communication behavior when they know they are being recorded.	Completed by trained RA off of Audio: SEGUE checklist for communication completed by research team (Appendix A-2) ²⁵ , comparing randomly sampled visits in Arm 2 vs Arm 3.
2B: Providers obtain higher scores on measures of attention to patient contextual factors essential to care planning when they know they are being recorded.	4C for contextualization of care ³⁴ , comparing randomly sampled visits in Arm 2 vs Arm 3.

As noted earlier, the PAM will be completed over the phone by the RA initially at one week after the visit (this will be extended to 10-14 days if it turns out a substantial number of patients listen to the audio more than one week after the visit).

Table 4.1 lists the calculated power for the intention-to-treat analyses for Hypotheses 1A-1C by outcome. These analyses are based on data from 1029 combined primary care and diabetes clinic visits each in Arms 1 and 2 (i.e. sample size 2058), except for measuring the effect of OAA on Hgb A1c (in 1C) which is based only on 202 diabetes clinic visits each in Arms 1 and 2 (total 404). For patient activation (1A), we assume veterans with no audio access will have a mean PAM score of 56 and standard deviation of 19.5, based on a 2016 national study of VA health care users;³⁵ clinically meaningful differences in activation have been described as 4-6 points.³⁶ Since testing hypothesis 1A requires a phone call to administer the PAM, we will randomly contact 924 participating subjects, an average of 9 calls/week across sites, which will achieve 80% power, instead of calling all 2058 subjects. Baseline rates of each undesirable outcome for 1B are derived from our previously published study in the VA using recordings without provider awareness or patient access (as in Arm 3), and we expect to find an odds ratio of 0.5 for each outcome when patients have access to audios.¹⁴ Baseline rates of each undesirable outcome for 1C are derived from the data warehouse (Chicago and Cleveland facilities – see table 3, above).

Table 4.1: Expected differences and power for planned intention-to-treat analyses for hypothesis 1A-1C

Hypothesis	Outcome	Baseline without audio available	Expected with audio available	Sample size	Power

		(Arm 2)	(Arm 1)	(total)	
1A	Patient activation (PAM 0-100 score)	56.0	60.0	924	80%
1B	Visit no-show rate	7%	4%	2058	95%
	Medication Proportion of days not covered	13%	7%	2058	80%
1C	Hgb A1c > 8 with repeat in < 6 Mo	66-70%	33-35%	404	80%
	Most Recent SBP>140 or DBP>90* with repeat in < 6 Mo	39%	24%	2058	99%

Also, while not included in Table 4.1, because it is not a primary objective of Aim 1, we will explore whether OAA is associated with fewer ED visits and hospitalizations. With the current sample size, we will in fact have 80% power to detect a decrease in inpatient admissions from 14%, the 2018 rate in our study population, to 9%.

Table 4.2 lists the calculated power for the analyses for Hypothesis 2A and 2B (comparisons of Arm 2 vs. Arm 3) based on actual Veteran visits by outcome. Baseline SEGUE scores are based on SEGUE's validation study among general internists (mean 17.5, sd 1.77); that study found that medical students in a skills lab achieved mean SEGUE scores of 21.1 (sd 2.1), and we take that as our minimal expected level of improvement from knowledge that one is being observed. Baseline rates of contextual probing and planning are based on our prior study in the VA using recordings without provider awareness or patient access (as in Arm 3), and incorporate the expectation that contextual red flags suitable for probing will be present in 2/3 of encounters and contextual factors that should be incorporated in planning will be present in 1/4 of encounters overall.¹⁴ Expected increases in probing and planning are based on odds ratios from our prior study comparing these measures in undercover visits to providers with the same cases presented to medical students in a testing setting (and are thus conservative measures of how much better providers would likely perform if they were aware vs. unaware they were being tested).¹³ To obtain at least 80% power for each of these comparisons, we will randomly sample 250 primary care clinic visits (from 827 Arm 2 primary care visits), and enroll all 250 primary care visits in Arm 3 for the SEGUE and 4C coding processes. For 4C, we expect 168 visits/arm with red flags suitable for probing and 63 visits/arm with contextual factors suitable for planning.

Table 4.2: Expected differences and power for planned analyses for hypotheses 2A and 2B

Outcome	Baseline (doctor unaware, n=250)	Expected (doctor aware, n=250)	Sample size (total)	Power
SEGUE provider score	17.5	21	500	99%
Contextual probing rate ^{13,26}	32%	47%	500	80%
Contextual	59%	82%	500	82%

planning rate ^{13,26}				
--------------------------------	--	--	--	--

All effects measured in Aim 1 and 2 will be adjusted for patient sociodemographic characteristics which will be obtained from the CDW (including age, gender, and race) or from administering the REALM-SF to assess literacy. Internet access, for those in the intervention arm, will be ascertained by census track using geocoding of patient addresses, based on FCC data, a method developed by Perzynski et al.^{37,38}

Aim 3:

Qualitative work will address safety, burden and value (as operationally defined in table 1, pp 17-18 above) in regard to adoption and implementation of OAA. This analysis will be based on the data collected utilizing the instruments referenced in table 1 and contained in the appendices: the surveys of both patients and providers about their experience participating in an OAA program. (for patients: A-1, A-7, A-8; for providers: A-2, A-3); the provider focus groups about their experience participating in an OAA program. (A-4, A-5); and structured interviews with facility leaders about their experiences with the OAA program. (A-6)

Data will be analyzed using thematic synthesis of leadership interviews, focus groups and patient surveys by 2 qualitative analysts (SB and ABC) with experience in qualitative methodology and ready access to qualitative data analysis computer software. We will create an a priori framework that includes safety, burden and value on three levels: provider participant, Veteran, and leadership. Further creation of codes and themes will be iterative. To ensure rigor and validity of findings each analyst will independently code and develop emerging themes. Each theme will be discussed between the two analysts until consensus is reached.

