3.0 Objectives

- Describe the study's purpose, specific aims, or objectives.
- State the hypotheses to be tested.

In this study, we will test our model for the purpose of delineating the extent to which OAA can bring value to patient care in VHA. We plan to control for demographic factors, namely: age, sex, race, health literacy, and internet access. The project will be conducted in primary care and one specialty clinic: diabetes. We select diabetes because of its high prevalence in Veterans, the presence of a specific marker of disease control (Hgb A1C), and that disease management now relies on a growing number of medications and dietary interventions that can be complex and overwhelming for patients. OAA, hence, may offer substantial benefits to patients and their caregivers and, if it does, the effect should be captured by falling Hgb A1c levels among those with baseline poor disease control. As noted, we also plan to study the impact of OAA on uncontrolled BP, but that data can be collected entirely in primary care given the very high prevalence rate.

This study has three aims, with the first two designed to test measurable hypotheses. The third is qualitative:

Aim 1: Assess the impact of an open access audio program on two behaviors (patient activation, treatment plan adherence), and two chronic condition measures (glycosylated hemoglobin, blood pressure). Secondary analysis will descriptively measure effect size on ED visits and hospital admissions.

Hypotheses:

- 1A: OAA increases patient activation.
- 1B: OAA increases care plan adherence, including fewer no-shows and more on-time refills.
- 1C: OAA reduces Hgb A1c and BP

Aim 2: Assess the impact of open access audio on provider communication behavior and on their attention to patient contextual factors (i.e. individual Veterans needs and circumstances relevant to planning effective care).

Hypotheses:

- 2A: Providers obtain higher scores on measures of communication behavior when they know they are being recorded.
- 2B: Providers obtain higher scores on measures of attention to patient contextual factors essential to care planning when they know they are being recorded.

Aim 3: Assess patient, provider, and leadership perceptions of the extent to which the program is safe, not burdensome, and worthwhile at both the start and at two years into the program.

- Indicate the relevance to Veterans and the VA

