For assessing provider behavior change based on awareness that the patient may get the audio recording and listen to it to better understand their care, we are focusing on both the process and content of the interaction. We selected SEGUE both because of its high evidence for concurrent and construct validity, and inter-rater reliability, and because it can be scored by an independent third party off of audio using a checklist.²⁷ Whereas SEGUE is a process measure (how effectively a provider communicates without regard to the content of the discussion), 4C is a content measure, i.e. whether they follow up on what the patient needs regardless of how they go about it. 4C is coded by a trained RA with access to the medical record and audio recording; the RA documents clues that a patient is struggling with life issues complicating their care ("contextual red flags"), whether the provider asks about them ("contextual probes"), whether the patient reveals the underlying life challenges ("contextual factors") and, if so, whether the physician addresses them ("contextualized care").²⁸ Contextual red flags are specific pre-determined variable extracted both from the medical record (including specific thresholds for missed appointments, emergency department visits, and medications that have not been refilled). 4C has strong published evidence for both construct validity and inter-rater reliability (90%),²⁶ and contextualized care significantly predicts a range of favorable patient health care outcomes.¹⁴ Notably, we have observed that physicians are more likely to contextualize care when they know they are being recorded.¹³ We have previously documented that communication performance and contextualization of care are separate constructs that do not correlate -- so must both be measured to fully assess patient centered provider behaviors.²⁹ Note that at the time of the coding, including completion of the SEGUE instrument, the audio coder will only have access to the designated codes for provider and patient, which will be utilized for tracking purposes. This is because the first step when audio recordings are uploaded following each encounter is to assign them codes with provider and patient names stored separately to a cross walk file.

Audio recording technology

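### The hypothesis 1B models leave out each patient's own pre-visit attendance and refill record, which costs some efficiency but not validity

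*Combined protocol and SAP*

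**What the plan says.** Section 5.6 (Aims 1 and 2) sets one model for every hypothesis: mixed linear or logistic regression "with a fixed effect of study arm, VA site, and primary vs. secondary care setting, and a random effect of provider".

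Other variables can enter by two routes:
- After balance tests on patient characteristics: "if any variables differ significantly among arms, we will include them as covariates in the regression models".
- By the statement after Table 4.2: "All effects measured in Aim 1 and 2 will be adjusted for patient sociodemographic characteristics which will be obtained from the CDW". This covers age, gender and race, with literacy from the REALM-SF. Internet access is to be obtained for the intervention arm.

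Section 3.0 gives a matching list: "We plan to control for demographic factors, namely: age, sex, race, health literacy, and internet access". None of these places names earlier attendance or earlier refill behaviour.

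Table 4 takes both 1B outcomes from the data warehouse. Table 3 reports the same two measures for these clinics in 2018, from the same source: PDC 88% and 84%, RVA 93% and 94%. Its footnote defines PDC as the "proportion of days patients had pills to cover medication needs based on refill rate over a 120 day interval". Section 5.1 also treats adherence history as informative: the 4C red flags are taken from the medical record, "including specific thresholds for missed appointments, emergency department visits, and medications that have not been refilled".

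**The concern.** How a patient attended and refilled before the index visit is likely to predict how they do so afterwards, and plausibly better than age, sex, race or literacy do. The plan commits to adjusting for the weaker predictors and leaves out the one closest to the outcome. The balance-test rule does not repair this. A covariate earns its place by predicting the outcome, not by a significant difference between arms, and a modest, non-significant imbalance in prior adherence would leave it out.

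Hypothesis 1B is one of three under Aim 1. At stake is how precisely adherence is estimated, and how much power remains if the true effect is smaller than the expected odds ratio of 0.5.

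**Working it through.** **Inputs.** From Table 4.1 and the text above it: 1029 per arm; no-show 7% versus 4%, stated power 95%; days not covered 13% versus 7%, stated power 80%; expected odds ratio 0.5. Assumed, because not stated: two-sided 5%, no allowance for provider clustering, and the correlation r between pre- and post-visit values.

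**Step 1: the plan's own figures.**

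*No-show.* Pooled standard error √(2 × 0.055 × 0.945 / 1029) = 0.01005; unpooled √((0.07 × 0.93 + 0.04 × 0.96) / 1029) = 0.01003. Power = Φ((0.03 − 1.96 × 0.01005) / 0.01003) = Φ(1.027) = 84.8%, not 95%. With an odds ratio of exactly 0.5 (7% to 3.6%) it is 92.7% two-sided and 96.2% one-sided.

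*Days not covered.* As yes/no outcomes, 13% versus 7% gives 99.5%, not 80%. As a continuous outcome, 80% power would need

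SD = 0.06 / ((1.960 + 0.842) × √(2/1029)) = 0.486.

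A variable between 0 and 1 with mean 0.13 cannot have an SD above √(0.13 × 0.87) = 0.336. Even at that ceiling in both arms, power is 98.2%. Matching 80% would take an unstated design effect of about 2.6 (1029 / 392, where 392 per arm gives 80%).

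Neither stated figure is reproduced at two-sided 5%, and the 80% is not a usable starting point for a power gain.

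**Step 2: PDC with the pre-visit value added (linear model).** Residual variance falls by the factor 1 − r², so the interval narrows by 1 − √(1 − r²). The total N that would carry the information of 2058 unadjusted patients is 2058 × (1 − r²).

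| r (assumed) | Interval narrows by | Equivalent N |
|---|---|---|
| 0.2 | 2.0% | 1976 |
| 0.3 | 4.6% | 1873 |
| 0.5 | 13.4% | 1544 |

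With power already at 98% or more at the printed rates, the benefit is precision.

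**Step 3: no-show with the pre-visit rate added (logistic model).** The factor 1 − r² belongs to the linear model and does not carry over, so this was simulated: 7% versus 4%, 1029 per arm, one later visit, 5 or 10 prior visits, 600 runs per setting, both models fitted to the same data, provider clustering not modelled. Monte Carlo error is about 1.5 points on each power.

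| Prior/later correlation | Power without | Power with | Gain (points) |
|---|---|---|---|
| 0.14 | 86.5% | 86.3% | −0.2 |
| 0.18 | 83.8% | 85.3% | 1.5 |
| 0.28 | 81.2% | 84.3% | 3.2 |
| 0.33 | 84.5% | 87.3% | 2.8 |
| 0.40 | 84.8% | 88.7% | 3.8 |
| 0.44 | 86.5% | 94.0% | 7.5 |

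A second set of runs, with 4 to 8 prior visits, gave about 0 to 1 point at a within-patient intraclass correlation of 0.05 to 0.10 and 3 to 5 points at 0.20.

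The standard error of the log odds ratio does not fall. Unadjusted it is √(1/(1029 × 0.0651) + 1/(1029 × 0.0384)) = 0.201. In simulation it went from 0.202 without the covariate to between 0.203 and 0.228 with it. Power rises because the conditional odds ratio moves further from 1.

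**The case against.** The strongest reply is that nothing here is wrong: randomisation protects the comparison and the model is a conventional one. That stands, and it makes this a refinement.

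Four further points deserve weight.

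- *The gain may be small.* No document supplies a correlation. With few visits per patient, past attendance may predict later attendance only weakly, and then the no-show gain is 0 to 2 points. This stands.
- *Large gains.* A reader might start from the stated 80% for PDC and infer a substantial power loss, for example 80% rising to 89.9% at r = 0.5. That starting point needs an SD no proportion with this mean can have. A reader might also apply the 5% or 13% narrowing to the no-show odds ratio; in a logistic model that interval does not narrow.
- *Availability.* A reader might take Table 3 to show that a prior value exists for every randomised patient. Table 3 holds clinic aggregates, there are no exclusion criteria, walk-in recruitment is allowed, and 4C history is read from the record for a sample. Some patients will have no earlier prescriptions or scheduled visits.
- *Other safeguards.* The balance-test rule covers patient differences beyond demographics, so a large imbalance in prior adherence could bring it in. It does not name that variable, however, and depends on a significant test. Section 6.0 mentions a separate Data Analysis Plan approved by the DSMB, which is not among these documents. It may name the covariate; section 5.6 does not.

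**Conclusion.** The omission is real: sections 3.0 and 5.6 commit to demographics and literacy but not to the patient's own earlier RVA or PDC. The consequence is lost efficiency. A reader might infer bias, or an invalid 1B test, but the documents support neither.

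Under the assumptions above, the size is modest: an interval about 2% to 13% narrower for PDC treated as continuous (r from 0.2 to 0.5), and roughly 0 to 7 points of power for no-shows from a base of about 85%. If the sponsor's 80% for PDC rests on a design effect that the plan does not state, there would be some PDC power to gain as well; that cannot be judged from the documents. The mismatch between the two 1B power figures and their printed rates is a separate matter. The change is worth making because it costs little, not because the analysis fails without it.

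**What to change.** In section 5.6, pre-specify for the 1B models, regardless of any balance test, the patient's value from the data warehouse before the index visit:
- refills: PDC over the 120 days before the visit, matching the Table 3 definition;
- no-shows: RVA over a fixed look-back, for example 12 months;
- both: a missing-history indicator for patients with no prior prescriptions or scheduled visits.

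Report a standardised (marginal) no-show difference between arms beside the conditional odds ratio. If the separate Data Analysis Plan already names these covariates, bring section 5.6 into line with it.

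The cost is a few sentences of analysis text and a longer look-back in an extraction already planned, with no patient contact. The downsides are a missing-history category to handle and an odds ratio that is conditional on prior attendance, which the marginal difference offsets.

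### The 1B adherence outcomes have no stated analysis row and no patient-level variance, and their printed powers do not follow from Table 4.1's own rates and sample size

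*Combined protocol and SAP*

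**What the plan says.** All references are to section 5.6 Data Analysis of the combined protocol and SAP unless stated otherwise.

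- **Outcomes.** Section 5.1 makes the no-show rate the inverse of Return Visit Adherence (RVA). The Table 3 footnotes define RVA as "The percentage of all visits scheduled to any clinics by patients seen in these clinics in 2018" and proportion of days covered (PDC) as "proportion of days patients had pills to cover medication needs based on refill rate over a 120 day interval".
- **Model.** Every hypothesis is tested by "mixed-effect linear or logistic regression as appropriate for the outcome". Arm, facility and type of clinic enter as fixed terms. The single random term listed is "a random effect of provider to accommodate clustering of visits within providers". Sociodemographic adjustment is added after Table 4.2. No patient term is named. Interest lies in the "direction, magnitude, and significance of the regression coefficient associated with study arm", but no alpha or sidedness is given.
- **Unit of allocation.** Patients are randomised, in blocks within clinic type (section 5.1).
- **Power.** The analyses rest on "1029 combined primary care and diabetes clinic visits each in Arms 1 and 2 (i.e. sample size 2058" in total. Table 4.1 gives the no-show rate as 7% versus 4% with 95% power, and "Medication Proportion of days not covered" as 13% versus 7% with 80% power, both at N = 2058. The text expects an odds ratio of 0.5 for each.
- **Not stated for 1B.** The analysis row, the follow-up window for no-shows, whether each outcome gets a linear or a logistic model, and any SD or within-patient correlation.

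**The concern.** A patient with several later appointments contributes several attended or missed visits, and these are likely to be correlated because some people miss appointments habitually. Arm is assigned to the patient, so between-patient variation sets the true standard error of the Arm 1 versus Arm 2 contrast. A provider random effect does not capture it: both arms will usually occur within a provider, and appointments at any clinic need not be with the index provider.

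The text leaves a visit-row analysis open. It speaks of visits clustered within providers, labels the outcome a visit no-show rate, and states the target as an odds ratio. An analyst could follow it literally, fit logistic regression to visit rows with a provider effect alone, and obtain a standard error that is too small. The stake is a false-positive adherence finding.

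The second matter is that Table 4.1 sets visit-level and day-level percentages against a count of patients, so it is unclear what calculation produced the two printed powers.

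**Working it through.** **Inputs from the documents:** 1029 per arm; 7% versus 4%; 13% versus 7%; odds ratio 0.5. **Assumed:** two-sided alpha 0.05; m scheduled visits per patient; within-patient correlation (ICC).

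**1. Attempt to reproduce the printed powers, one yes/no per patient.**
Power = Φ{[d − 1.96·SE0]/SE1}, with SE0 = √(2·p̄(1−p̄)/n) and SE1 = √([p1(1−p1)+p2(1−p2)]/n).

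- No-show: d = 0.03, p̄ = 0.055, SE0 = √(0.10395/1029) = 0.01005, SE1 = √(0.1035/1029) = 0.01003. Power = Φ(1.03) = **84.8%**, against 95% printed.
- Days not covered: d = 0.06, p̄ = 0.10, SE0 = √(0.18/1029) = 0.01323, SE1 = √(0.1782/1029) = 0.01316. Power = Φ(2.59) = **99.5%**, against 80% printed.

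Variants:

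| Method | No-show | Days not covered |
|---|---|---|
| Two-sided, printed rates | 84.8% | 99.5% |
| Continuity-corrected | 82.4% | 99.4% |
| Arcsine | 85.4% | 99.6% |
| One-sided | 91.0% | 99.8% |
| Unrounded OR 0.5 (3.63%; 6.95%), two-sided | 92.7% | 99.6% |
| Unrounded OR 0.5, one-sided | 96.2% | 99.8% |
| Printed | 95% | 80% |

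The two discrepancies run in opposite directions. At the printed rates, 95% for no-show needs 1498 per arm, more than the 1029 available. For days not covered, 80% needs only 392 per arm, which implies a deflation of 1029/392 = 2.6. One common clustering allowance cannot raise the first and lower the second.

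**2. PDC as one continuous value per patient.**
Power = Φ{0.06/(SD·√(2/1029)) − 1.96}. The largest SD possible for a 0–1 variable with mean 0.13 is √(0.13·0.87) = 0.336. At that SD the standard error is 0.336·0.0441 = 0.0148, and power = Φ(4.05 − 1.96) = 98%. At SD 0.30 it is 99.5%. To reach 80% the SD would have to be 0.06/(0.0441·2.80) = 0.486, which is impossible.

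**3. Type I error if visits are rows and no patient term is fitted.**
Design effect DE = 1 + (m−1)·ICC. Actual type I error = 2·[1 − Φ(1.96/√DE)].

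| m | ICC 0.1: DE, type I | ICC 0.2: DE, type I |
|---|---|---|
| 2 | 1.1, 6.2% | 1.2, 7.4% |
| 3 | 1.2, 7.4% | 1.4, 9.8% |
| 4 | 1.3, 8.6% | 1.6, 12% |
| 5 | 1.4, 9.8% | 1.8, 14.4% |
| 6 | 1.5, 10.9% | 2.0, 16.6% |

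Beta-binomial simulation agrees. At ICC 0.1, ignoring the patient gave 7.8% for 3 visits and 9.5% for 5; using patient-level variance gave 5.4% and 5.2%.

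**4. No-show power when the correlation is respected.**
Effective n per arm = 1029·m/DE. For m = 2 this is 2058/1.1 = 1871 (98%) at ICC 0.1, 2058/1.2 = 1715 (97%) at ICC 0.2, and 2058/1.5 = 1372 (93%) at ICC 0.5. All exceed the 85% for a single yes/no.

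**5. Origin of the baselines.**
Weighting Table 3 by clinic totals (34,036 and 12,833, sum 46,869) gives no-show (7%·34,036 + 6%·12,833)/46,869 = 6.7%, and days not covered (12%·34,036 + 16%·12,833)/46,869 = 13.1%. Both match the Table 4.1 baselines, although the text attributes the 1B baselines to a prior published study.

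**The case against.** The strongest reply is that the harmful reading is not the natural one. Section 5.2 recruits 1904 + 404 = 2308 patients. Removing the 250 in Arm 3 leaves 2058, so the 2058 visits are one index visit per patient, and the provider effect plausibly refers to clustering of those index visits. On that reading RVA and PDC are one value per patient, the choice of linear or logistic model as appropriate covers them, no patient term is needed, and type I error stays near 5%. The Table 3 footnotes describe the 2018 clinic populations and do not prescribe trial rows. Section 6.0 also mentions a data analysis plan approved by the monitoring board, which might settle the matter but is not part of the text reviewed. All of this stands, and it makes the inflation conditional. It does not remove the gap, because the text permits both a valid and an anti-conservative test of a named hypothesis.

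Three stronger readings are tempting and are not supported:

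- **That the 1B error rate is wrong as planned.** It is wrong only if visits (or days) are the rows, and the documents do not say that they are.
- **That Table 4.1 was computed with one yes/no per patient.** That method gives neither printed figure from the printed rates, and it cannot give 80% for PDC under any variant tried. A multi-visit calculation can land near 95% for no-show (three visits at ICC 0.5 gives 95.5%), but no such inputs are stated.
- **That the missing patient term overstates power, so the trial is too small.** Handling several visits or a continuous PDC correctly gives more power than a single yes/no, and the PDC figure is understated.

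**Conclusion.** The point holds in two separate parts.

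First, the analysis row for 1B is unspecified and the only random effect is for provider. If visits were rows, type I error would be about 6% to 17% for 2 to 6 visits per patient at ICC 0.1 to 0.2. Visits per patient and ICC are assumptions; the documents give neither.

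Second, and whichever row is chosen, the printed powers of 95% and 80% do not both follow from the printed rates and N by any single method tried. The results are about 85% for no-show (93% with the unrounded odds ratio) and about 99.5% for days not covered, or at least 98% for a continuous PDC. These rest on an assumed two-sided 0.05.

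The first part does not cause the second. With all 2058 patients analysed, both outcomes exceed the 80% target. That depends on patients having a return visit to count: if only 80% did (assumed), no-show power with one yes/no per patient would be 76%.

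**What to change.** In the model description under Aims 1 and 2 of section 5.6:

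- **No-shows:** state the counting window, and analyse missed out of scheduled visits per patient with an overdispersed binomial model. Alternatively, keep visit rows and add a patient random intercept or patient-robust variance.
- **PDC:** state one row per patient, analysed as a continuous or fractional outcome.
- **Table 4.1:** recompute both 1B rows on those units, with alpha, sidedness, the SD for PDC, and the visits per patient and ICC for no-shows all stated.

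The cost is a few sentences and one recalculation, with no new data. Intervals will be slightly wider than from a naive visit-level analysis, and the printed powers will change. Settle this before the 1B data are analysed by arm, so that the row is not chosen with results in view.
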